#### 5.3 Response Assessment

#### 5.3.1 Evaluation of Best Overall Response

The best overall response is the best response recorded from the start of the study treatment until disease progression or the last response recorded, taking into account any requirement for confirmation and censoring rules regarding subsequent therapy. The patient's best overall response assignment will depend on the findings of both target and non-target disease and will also take into consideration the appearance of new lesions. Furthermore, depending on the nature of the study and the protocol requirements, it may also require confirmatory measurement.

## 5.3.2 Time Point Response

At each protocol specified time point, a response assessment occurs. Table 5.3.2-1 provides a summary of the overall response status calculation at each time point for patients who have measurable disease at baseline. When patients have non-measurable (therefore non-target) disease only, Table 5.3.2-2 is to be used.

Table 5.3.2-1: Time Point Response: Patients With Target (± Non-Target) Disease			
Target Lesions	Non-Target Lesions	New Lesions	Overall Response
CR	CR	No	CR
CR	Non-CR/non-PD	No	PR
CR	Not evaluated	No	PR
PR	Non-PD or not all evaluated	No	PR
SD	Non-PD or not all evaluated	No	SD
Not all evaluated	Non-PD	No	NE
PD	Any	Yes or No	PD

Table 5.3.2-1: Time Point Response: Patients With Target (± Non-Target) Disease			
Target Lesions	Non-Target Lesions	New Lesions	Overall Response
Any	PD	Yes or No	PD
Any	Any	Yes	PD

CR = complete response, PR = partial response, SD = stable disease, PD = progressive disease and NE = inevaluable

Table 5.3.2-2: Time Point Response: Patients with Non-target Disease Only		
Non-Target Lesions	New Lesions	Overall Response
CR	No	CR
Non-CR/non-PD	No	Non-CR/non-PD a
Not all evaluated	No	NE
Unequivocal PD	Yes or No	PD
Any	Yes	PD
CR = complete response, PD = progressive disease and NE = inevaluable		

<sup>a Non-CR/non-PD is preferred over SD for non-target disease since SD is increasingly used as endpoint for assessment of efficacy in some trials so to assign this category when no lesions can be measured is not advised.

## 5.3.3 Best Overall Response

Best response determination of complete or partial response requires confirmation: Complete or partial responses may be claimed only if the criteria for each are met at a subsequent time point of  $\geq 4$  weeks (28 days) later. In this circumstance, the best overall response can be interpreted as in Table 5.3.3-1. When SD is believed to be best response, it must meet the protocol specified minimum time from the date of first treatment or randomization date.

For example, if the first scheduled follow-up imaging visit is Week 6 ( $\pm$  7 days) for a particular protocol, a Best Response of SD can only be made after the subject is on-study for a minimum of 6 weeks (42 days) minus 7 days, for an absolute minimum time on-study of 35 days from the reference start date (reference date is considered Day 1 on study). If the subject is not on-study for at least this amount of time, any tumor assessment indicating stable disease before this time period will have a Best Response of NE unless PD is identified.

**Special note on response assessment:** When nodal disease is included in the sum of target lesions and the nodes decrease to 'normal' size (< 10 mm), they may still have a measurement reported on scans. This measurement should be recorded even though the nodes are normal in order not to overstate progression should it be based on increase in size of the nodes. As noted earlier, this means that patients with CR may not have a total sum of 'zero' on the case report form (CRF).

Table 5.3.3-1:	Table 5.3.3-1: Best Overall Response (Confirmation of CR and PR Required)		
Overall Response First Time Point	Overall Response Subsequent Time Point	Best Overall Response	
CR	CR	CR	
CR	PR	SD, PD OR PR a	
CR	SD	SD provided minimum criteria for SD duration met, otherwise, PD	
CR	PD	SD provided minimum criteria for SD duration met, otherwise, PD	
CR	NE	SD provided minimum criteria for SD duration met, otherwise, NE	
PR	CR	PR	
PR	PR	PR	
PR	SD	SD	
PR	PD	SD provided minimum criteria for SD duration met, otherwise, PD	
PR	NE	SD provided minimum criteria for SD duration met, otherwise, NE	
NE	NE	NE	
CR = complete respo	CR = complete response, PR = partial response, SD = stable disease, PD = progressive disease, and		
NE = inevaluable			

<sup>a If a CR is truly met at first time point, then any disease seen at a subsequent time point, even disease meeting PR criteria relative to baseline, makes the disease PD at that point (since disease must have reappeared after CR). Best response would depend on whether minimum duration for SD was met. However, sometimes 'CR' may be claimed when subsequent scans suggest small lesions were likely still present and in fact the patient had PR, not CR at the first time point. Under these circumstances, the original CR should be changed to PR and the best response is PR.

#### 5.3.4 Confirmation Scans

Verification of Response: To be assigned a status of CR or PR, changes in tumor measurements must be confirmed by consecutive or subsequent repeat assessments that should be performed no less than 28 days after the criteria for response are first met. Subsequent documentation of a CR may provide confirmation of a previously identified CR even with an intervening NE or PR (eg, CR NE CR or CR PR CR). Subsequent documentation of a PR may provide confirmation of a previously identified PR even with an intervening NE or SD (eg, PR NE PR or PR SD PR). However, only one (1) intervening time point will be allowed between PR/CRs for confirmation.

Verification of Progression: Progression of disease should be verified in cases where progression is equivocal. If repeat scans confirm PD, then progression should be declared using the date of the initial scan. If repeat scans do not confirm PD, then the subject is considered to not have progressive disease.

Protocol Amendment No.: 07

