# 4 OBJECTIVES AND ENDPOINTS

Table 4-1: Objectives and Endpoints - Part 1

Objectives	Endpoints
Primary	
To characterize safety, tolerability, and DLTs, and to determine the RP2D of BMS-986253 administered in combination with nivolumab, or in combination with nivolumab and ipilimumab in participants with advanced solid tumors.	Incidence of AEs, SAEs, AEs meeting protocol- defined DLT criteria, and AEs leading to discontinuation, death, and laboratory abnormalities.
Secondary	

 
To evaluate the preliminary efficacy of BMS-986253 in combination with nivolumab in participants with advanced solid tumors using RECIST v1.1.
 
To characterize the PK and immunogenicity of BMS-986253 when administered in combination with nivolumab, or in combination with nivolumab and ipilimumab in participants with advanced solid tumors.
 
To assess serum IL-8 levels at baseline (ie, screening) and changes in IL-8 levels on treatment.
 
	
 
ORR and DOR per RECIST v1.1 per investigator.
 
Summary measures of PK parameters and incidence of ADA to BMS-986253.
 
Summary measures of IL-8 and change (or percent change) from baseline in IL-8 on treatment.
 

Abbreviations: ADA, anti-drug antibody; AE, adverse event; DLT, dose-limiting toxicity; DOR, duration of response; EOT, end of treatment; ORR, objective response rate; PK, pharmacokinetic(s);

Protocol Amendment No.: 07

RECIST, Response

Evaluation Criteria in Solid Tumors; RP2D, recommended Phase 2 dose; SAE, serious adverse event.

[figure not shown]
Table 4-2: Objectives and Endpoints - Part 2

	Objectives	Endpoints
Pri	imary	
•	To compare the ORR of BMS-986253 plus nivolumab plus ipilimumab with placebo plus nivolumab and ipilimumab using RECIST v1.1.	ORR based on BICR assessments per RECIST v1.1 in all randomized participants.
Sec	condary	
•	To estimate PFS of BMS-986253 plus nivolumab plus ipilimumab and placebo plus nivolumab and ipilimumab in participants with advanced melanoma using RECIST v1.1 (regardless of baseline serum IL-8 levels).	mPFS and PFS hazard ratio based on BICI assessments per RECIST v1.1.
•	To compare the safety of BMS-986253 plus nivolumab plus ipilimumab with placebo plus nivolumab plus ipilimumab in participants with advanced melanoma.	discontinuation, death, and laborator

Protocol Amendment No.: 07

Date: 17-May-2024 68

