## 9.4 Efficacy Assessments

Following the database lock for the final analysis, efficacy will no longer be assessed. Imaging should be performed per standard of care at the discretion of the treating physician.

Efficacy assessments for the anti-tumor activity of BMS-986253, in combination with nivolumab or in combination with nivolumab and ipilimumab, will use investigator assessed tumor measurements, per RECIST v1.1 (Appendix 8).

Assessments of partial response (PR) and CR must be confirmed at least 4 weeks after initial response. Changes in tumor measurements and tumor responses will be assessed by the investigator per study design using RECIST v1.1 criteria (Appendix 8). Investigators will also report the number and size of new lesions that appear while on study. The timepoint of tumor assessments will be reported on the eCRF based on the investigator's assessment.

A BICR will be utilized in this study for determination of BICR-assessed endpoints. The BICR will review all available tumor assessment scans for all treated participants until the final analysis is completed. Details of BICR responsibilities and procedures will be specified in the BICR charter.

A Best Overall Response of SD requires a minimum of 49 days on study from the date of first dose to the date of the first imaging assessment.

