#### Endpoint **Statistical Analysis Methods** BICR-assessed ORR will be used to compare ORR between 2 treatment groups. The ORR is defined as the proportion of participants whose BOR associated odds ratio and CI will also be is either CR or PR in the population of interest. calculated. BOR for a participant will be assessed per RECIST v1.1. BOR per RECIST v1.1 is defined as the best response designation recorded between the date of the first dose and the date of first objectively documented progression per RECIST v1.1 or the date of subsequent therapy, whichever occurs first. For participants who continue treatment beyond progression per RECIST v1.1 or begin subsequent therapy, the BOR should be determined based on response designations recorded up to the time of the initial progression or subsequent therapy, whichever occurs first. For participants without documented progression or subsequent therapy, all available response designations should contribute to the BOR assessment. DOR Median duration of response using method and corresponding two-sided 95% CI DOR for a participant with a BOR of CR or PR is defined as the time between the date of first response and the date of the first objectively documented tumor progression per RECIST v1.1 or death, whichever occurs first. Participants who die without a reported progression will be considered to have progressed on the date of their death. Participants who did not progress or die will be censored on the date of their last evaluable tumor assessment. Participants who did not have any on-study tumor assessments and did not die will be censored on the date of first dose. Participants who started any subsequent anticancer therapy, including tumor-directed radiotherapy and tumor-directed surgery, without a prior reported progression will be censored at the last evaluable tumor assessment prior to initiation of the subsequent anticancer therapy.

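### Appendix 8 gives conflicting best overall responses for the sequence CR, PR, CR when disease is unequivocally seen again at the middle scan after a true CR

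*Combined protocol and SAP*

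**What the plan says.** The Part 2 primary endpoint (Section 4, Table 4-2) is "ORR based on BICR assessments per RECIST v1.1 in all randomized participants". Response is classified by Appendix 8, the protocol's modified RECIST 1.1. These places decide how CR, PR, CR is scored:

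- **Appendix 8, Section 5.3.4 (Confirmation Scans):** "Subsequent documentation of a CR may provide confirmation of a previously identified CR even with an intervening NE or PR". CR PR CR is listed as an example, and one intervening time point is allowed.
- **Appendix 8, Table 5.3.3-1:** a CR followed by a PR gives SD, PD or PR. CR is not among the outcomes.
- **Footnote a to that table, CR truly met:** "any disease seen at a subsequent time point, even disease meeting PR criteria relative to baseline, makes the disease PD at that point", and "Best response would depend on whether minimum duration for SD was met".
- **Footnote a, CR claimed in error because small lesions were probably still there:** "the original CR should be changed to PR and the best response is PR".
- **Table 10.3.1-2:** best overall response is the "best response designation recorded between the date of the first dose and the date of first objectively documented progression", or the start of subsequent therapy if that comes sooner. PFS runs to the same first documented progression, or to death.
- **Section 9.4:** "A Best Overall Response of SD requires a minimum of 49 days on study from the date of first dose".

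**The concern.** Section 5.3.4 and the first branch of footnote a give opposite answers for one situation: a true CR, disease unequivocally visible again at the next scan but still small enough to be read as PR against baseline, then CR once more. One rule passes over the middle scan and confirms the CR. The other calls that scan progression, which closes the response window before the second CR can count.

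At stake is whether the participant is a responder in the primary ORR, whether a PFS event is recorded, and whether the participant enters the duration-of-response analysis. If the choice is left to a reader or a programmer, it may differ between cases or be made after the data have been seen.

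**Working it through.** The plan states no figure on this point, and the Part 2 size is redacted, so there is nothing to reproduce. The check is a trace of one sequence through the rules, followed by its size under assumed arm sizes.

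**Sequence.** CR at Week 8, PR at Week 16, CR at Week 24. This fits the 8-weekly imaging schedule of Section 9.4.1. The two CRs are 16 × 7 = 112 days apart, beyond the 28 days needed for confirmation, with one scan between them.

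**SD minimum.** The first scan is due at 8 weeks with a 7-day window: 8 × 7 − 7 = 49 days. Any first scan inside its window therefore meets the SD minimum.

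| Rule applied | Status at Week 16 | Best overall response | Responder | PFS event at Week 16 |
|---|---|---|---|---|
| Section 5.3.4 | PR | CR | yes | no |
| Footnote a, CR truly met | PD | SD if first scan at day 49 or later, otherwise PD | no | yes |
| Footnote a, first CR relabelled PR | PR | PR | yes | no |

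In the second row the window in Table 10.3.1-2 closes at Week 16. The only earlier designation is an unconfirmed CR, and the Week 24 CR falls outside the window. Progression is the status of the Week 16 scan; the best overall response is normally SD.

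The first and third rows agree on ORR and PFS and differ only in the CR or PR category. For the primary endpoint, the conflict is between the first and second rows.

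**Where the rules are compatible.** Two cases raise no conflict:

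1. Table 5.3.2-1 scores target CR with non-target lesions not evaluated and no new lesion as PR. No disease has been seen, so footnote a is not triggered and Section 5.3.4 can apply.
2. Under Verification of Progression in Section 5.3.4, equivocal progression that repeat scans do not confirm is not progression. A clear Week 24 scan can serve as that repeat.

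An unequivocal new lesion is PD in Table 5.3.2-1, so it cannot be the middle PR. What remains is unequivocal return of disease already recorded at baseline.

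**Size.** One reclassified participant moves an arm's ORR by 1/n. With n assumed:

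- n = 30: 1/30 = 3.3 percentage points
- n = 60: 1/60 = 1.7 percentage points

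As an illustration only, assume 50 per arm, 15 control responders (30%, near the 29% and 31% cited in Section 5.4.8) and a pooled two-proportion z-test. With 25 experimental responders, z = (0.50 − 0.30)/√(2 × 0.40 × 0.60/50) = 2.04 and two-sided p = 0.041. With 24, z = (0.48 − 0.30)/√(2 × 0.39 × 0.61/50) = 1.85 and p = 0.065. The test, the arm size and the counts are all assumptions.

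**The case against.** The best defence is that the provisions do different jobs. Table 5.3.3-1 deals with pairs of scans, whereas Section 5.3.4 alone deals with an interrupted sequence, and its wording permits confirmation without requiring it. A reader who judges that disease has returned may still apply footnote a. Section 5.3.4 also has a legitimate use where the middle PR reflects a missed non-target assessment, and unconfirmed equivocal progression is already cancelled. Operational detail is left to the BICR charter, and the SAP is to be finalised before database lock; the charter is not available here and may settle the matter.

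Much of this stands, and it narrows the problem to unequivocal reappearance. It does not remove it. Section 5.3.4 is not limited to the harmless cases, a permissive rule does not rank itself against a categorical one, and a charter that simply follows Appendix 8 would inherit both rules.

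A reader might infer that no PR can ever follow a standing CR under footnote a, so that the Section 5.3.4 example is simply wrong. Table 5.3.2-1 shows otherwise. A reader might also infer that the lenient route favours the experimental arm. Under Section 9.4.2, central review is blinded to treatment arm, and nothing in the documents shows a directional effect.

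**Conclusion.** The inconsistency is real but narrow. For CR, PR, CR with disease unequivocally seen at the middle scan after a true CR, Appendix 8 supports both a responder without progression and a non-responder with a PFS event, and states no precedence.

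It would be too strong to say that the primary ORR and PFS in general turn on which page is used, or that three conflicting rules exist. Two of the three routes give the same ORR and PFS. The choice within footnote a, between relabelling the CR and calling progression, is a reader's judgement about the first scan and not a contradiction between passages.

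The actual effect cannot be quantified: the documents give no frequency for the sequence, and the arm size is redacted. The sequence is probably rare, possibly absent. The 3.3 to 1.7 points per participant rest on the assumed 30 to 60 per arm and apply only if a case occurs. The reason to act is that the rule defines a responder on the primary endpoint and can be settled cheaply before results are known.

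**What to change.** Keep the intervening PR in Section 5.3.4, but limit it to time points where no reappeared disease is seen (for example, target CR with non-target lesions not evaluated) or where equivocal progression was not confirmed. Add one sentence making footnote a govern whenever disease is unequivocally seen after a CR: if the CR was true, PD on that date; otherwise the earlier CR is relabelled PR.

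Removing the intervening PR altogether would go too far. A genuine CR interrupted only by a missed non-target assessment would then have no confirmation rule.

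Mirror the wording in the SAP, the BICR charter and the derivation program before database lock and unblinding. The cost is a sentence or two in each document and no new scans. The downside is that a few confirmed CRs may become PR or SD.

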## APPENDIX 9 CHILD-PUGH SCORE

Score	Points
Child-Pugh A	5 - 6
Child-Pugh B	7 - 9
Child-Pugh C	> 9

# **Scoring**

		Score	
Measure	1 Point	2 Points	3 Points
Ascites	Absent	Slight	Moderate
Serum bilirubin (mg/dl)	< 2.0	2.0 - 3.0	> 3.0
Serum albumin (g/dl)	> 3.5	2.8 - 3.5	< 2.8
PT prolongation or INR	< 4 sec < 1.7	4 - 6 sec 1.7 - 2.3	> 6 sec > 2.3
Encephalopathy grade	None	1 - 2	3 - 4

Abbreviations: INR = International normalized ratio; PT = prothrombin time.

# **Encephalopathy Grading**

Encephalopathy Grade	Clinical Definition
Grade 0	Normal consciousness, personality, and neurological examination
Grade 1	Restless, sleep disturbed, irritable/agitated, tremor, and impaired handwriting
Grade 2	Lethargic, time-disoriented, inappropriate, asterixis, and ataxia
Grade 3	Somnolent, stuporous, place-disoriented, hyperactive reflexes, and rigidity
Grade 4	Unarousable coma, no personality/behavior, decerebrate

Protocol Amendment No.: 07

Approved v 8.0 930120018 9.0

[figure not shown]
APPENDIX 10	NEW YORK HEART ASSOCIATION FUNCTIONAL CLASSIFICATION
NYHA Class	Patients with Cardiac Disease (Description of Heart Failure Related Symptoms)
Class I (Mild)	Patients with cardiac disease but without resulting in limitation of physical activity. Ordinary physical activity does not cause undue fatigue, palpitation (rapid or pounding heart beat), dyspnea (shortness of breath), or anginal pain (chest pain).
Class II (Mild)	Patients with cardiac disease resulting in slight limitation of physical activity. They are comfortable at rest. Ordinary physical activity results in fatigue, palpitation, dyspnea, or anginal pain
Class III (Moderate)	Patients with cardiac disease resulting in marked limitation of physical activity. They are comfortable at rest. Less than ordinary activity causes fatigue, palpitation, dyspnea, or anginal pain.
Class IV (Severe)	Patients with cardiac disease resulting in the inability to carry on any physical activity without discomfort. Symptoms of heart failure or the anginal syndrome may be present even at rest. If any physical activity is undertaken, discomfort is increased.

Reference: The Criteria Committee of the New York Heart Association. *Nomenclature and Criteria for Diagnosis of Diseases of the Heart and Great Vessels*. 9th ed. Boston, Mass: Little, Brown & Co; 1994:253-256.

[figure not shown]
## APPENDIX 11 COUNTRY SPECIFIC AMENDMENTS

[figure not shown]
# Germany and Any Other Countries Where Exclusion of HIV Positive Participants Is Locally Mandated

	Country-specific language
Section 6.2 Exclusion Criteria, Exclusion criterion 3) e)	"Known history of testing positive for human immunodeficiency virus (HIV) or known acquired immunodeficiency syndrome (AIDS)"to be replaced with "Positive test for HIV".

[figure not shown]

[figure not shown]
Protocol Amendment No.: 07

Protocol Amendment No.: 07

[figure not shown]

Date: 17-May-2024 252

Clinical Protocol CA027002 BMS-986253 Anti-IL-8

Protocol Amendment No.: 07

Clinical Protocol
BMS-986253
CA027002
Anti-IL-8

# APPENDIX 13 PROTOCOL AMENDMENT SUMMARY OF CHANGE HISTORY

Overall Rationale for Protocol Amendment 06, 17-May-2023

Section Number & Title	Description of Change	Brief Rationale
Table 2-2: Screening Procedural Outline (All Study Phases)		
Table 2-5: On-treatment Procedural Outline  Table 2-6: On-treatment Procedural Outline (Part 1C and Part 2 - BMS-986253 Q2W and Nivolumab and Ipilimumab Q3W)	Removed severe acute respiratory syndrome coronavirus 2 serology testing.	To align with revised Bristol- Myers Squibb Company (BMS
Table 2-7: Safety Follow-up Procedural Outline	c, c	guidelines.
Section 3.3.1: Safety Monitoring on Study Treatment		
Table 4-2: Objectives and Endpoints - Part 2		
Section 9.2.3: Follow-up of Adverse Events and Serious Adverse Events		

Protocol Amendment No.: 07

Section Number & Title	Description of Change	Brief Rationale
Section 9.8: Biomarkers		
Table 2-2: Screening Procedural Outline (All Study Phases)	Removed fasting requirement.	Fasting is no longer a requirement as it is not clinically necessary.
Table 2-2: Screening Procedural Outline (All Study Phases)  Table 2-3: On-treatment Procedural Outline (Part 1A and Cohorts 1B1 through 1B3 - BMS-986253 Q4W and Nivolumab Q4W)  Table 2-4: On-treatment Procedural Outline (Cohorts 1B4 through 1B6 - BMS- 986253 Q2W and Nivolumab Q4W)  Table 2-5: On-treatment Procedural Outline  Table 2-6: On-treatment Procedural Outline  Table 2-6: On-treatment Procedural Outline (Part 1C and Part 2 - BMS-986253 Q2W and Nivolumab and (pilimumab Q3W)  Table 2-7: Safety Follow-up Procedural Outline	Added serious adverse event reporting requirements. Clarified adverse event reporting.	Clarification and alignment throughout the protocol.

SUMMARY OF KEY CHANGES FOR PROTOCOL AMENDMENT 06		
Section Number & Title	Description of Change	Brief Rationale
Section 9.2.1: Time Period and Frequency for Collecting Adverse Event and Serious Adverse Event Information		
Table 2-2: Screening Procedural Outline (All Study Phases) Section 5.1.2: Screening Period Section 6.1: Inclusion Criteria	Clarified biopsy language. Revised inclusion criteria for pre-treatment biopsy for participants enrolled in Part 2.	To ensure data quality.  To improve study accessibility for participants in Part 2.
Table 2-2: Screening Procedural Outline (All Study Phases)	Specified timing of image acquisition.	Clarification.
Table 2-3: On-treatment Procedural Outline (Part 1A and Cohorts 1B1 through 1B3 - BMS-986253 Q4W and Nivolumab Q4W) Table 2-4: On-treatment Procedural Outline (Cohorts 1B4 through 1B6- BMS- 986253 Q2W and Nivolumab Q4W) Table 2-5: On-treatment Procedural Outline  Table 2-6: On-treatment Procedural Outline  Table 2-6: On-treatment Procedural Outline (Part 1C and Part 2 - BMS-986253 Q2W and Nivolumab and Ipilimumab Q3W) Section 5.1.1: Follow-up Section 5.1.5.1: Safety Follow-up Period	Specified end of treatment (EOT) definition. For participants who do not complete all scheduled cycles of therapy, the EOT visit will be the next visit following the last study dose. If the EOT visit occurs 30 days or more after receipt of the last dose, then the EOT visit and Follow-up 1 visit can be completed at the same time.	Clarification.
Table 2-7: Safety Follow-up Procedural Outline Section 5.1.5.3: Survival Follow-up Period	Clarified language for survival follow-up and safety follow-up.	To maintain alignment throughout the protocol.
Section 5.1: Overall Design Section 10.1.2: Part 1C	Added information about Cohort 1C1 and the impact of that data on Cohort 1C2.	To confirm the safety and evaluate the efficacy of the triplet regimen in participants with MSS and/or pMMR CRC.

Protocol Amendment No.: 07 Date: 17-May-2024

[figure not shown]
ate: 17-May-2024

Section Number & Title	Description of Change	Brief Rationale
	Added justification to open Part 1C2 for enrollment of approximately up to 10 participants with CRC.	
Section 5.1: Overall Design Figure 5.1-2: Study Design Part 1 Figure 5.1-3: Study Design Part 2 Section 5.5.2: Rationale for Part 1B Dosing Schedules and Maximum Administered Dose Section 5.5.4: Rationale for Nivolumab Dose Selection Section 5.5.5: Rationale for Ipilimumab Dose Selection Section 5.5.6: Rationale for Part 2 Dosing Schedules and Maximum Administered Dose/RP2D Section 7.4: Method of Treatment Assignment and Stratification Table 7.3-1: Dose, Frequency, Infusion Time, and Sequence of IPs	
 
Updated study designs with the number of participants enrolled as of publication of Protocol Amendment 06.
 
Identified the MTD/MAD of BMS-986253 as 3600 mg every 2 weeks (Q2W)
 
Updated Study Design Part 2 to reflect the RP2D.
 
Added a new section.
 
	To justify the selection of the RP2D for Part 2.
Section 5.1: Overall Design Figure 5.1-2: Study Design: Part 1	Updated the number of participants for Part A Cohort 1B1	Part A Cohort 1B1 enrolled a total of participants.
Section 5.1.2: Screening Period	Added "Repeat serum IL-8 testing will not be required if the previous sample was obtained within 42 days of study treatment initiation."	Clarification
Section 6.1: Inclusion Criteria	Clarified inclusion criterion 2) a) that participants must have radiographically measurable disease.  Added criterion 2) c) xii) (4) (a) with palliative radiation considerations.  Updated criterion 2 a) for screening requirements.  Updated criterion 2) c) vi) (2) with microsatellite instability status or mismatch repair information.	To clarify the inclusion criteria and improve readability.

SUMMARY OF KEY CHANGES FOR PROTOCOL AMENDMENT 06		
Section Number & Title	Description of Change	Brief Rationale
Section 6.2: Exclusion Criteria	Added exclusion criterion 3) i): History of HLH/macrophage activation syndrome (MAS).	
Section 7.6.8:	Added exclusion criterion 3) j): diseases related to chronic Epstein-Barr virus infections.	
Hemophagocytic Lymphohistiocytosis (HLH)	Added HLH as a dose-limiting toxicity that requires treatment discontinuation	
Section 7.6.8.1: HLH Management Approaches	Added new sections with background information about HLH and management of HLH.	
Table 7.3-1: Dose, Frequency, Infusion Time, and Sequence of IPs	Added footnote h to specify the infusion time.	Clarification and to maintain alignment throughout the protocol.
Section 7.4: Method of Treatment Assignment and Stratification	Corrected an error in the description of assigning the participant identifier number.  Removed description of replacing participants.	Correction. Participants will not be replaced in this way.
Section 10.3.4: Immunogenicity Analyses	Added "summary of anti-drug antibody (ADA) peak titer, ADA onset and duration, summary of select adverse events, by ADA status, summary of best overall response by ADA status."	To align with the updated immunogenicity statistical analysis plan.
Appendix 2: Study	Added sections:  BMS Commitment to Diversity in Clinical Trials	To align with BMS commitment to diversity in clinical trials.
Governance Considerations	Data Protection, Data Privacy, and Data Security	To comply with the European Union Clinical Trials Regulation requirement.

Protocol Amendment No.: 07 Date: 17-May-2024 Clinical Protocol
BMS-986253
CA027002
Anti-IL-8

